 initiated at a total daily dosage of 10 mg/kg per day.

Study design:

Type of the study: randomized controlled study.

The following data will be gathered and evaluated for all patients:

I-before intervention:

- Serum creatinine, Creatinine clearance. .1
- 24 hour urine protein, urine protein/creatinine ratio. .2
 - Urine analysis. .3
 - HBA1c. .4
 - HGB. .5
 - Uric acid and lipid profile. .6
 - Lupus serology. .7

II-after intervention: All patients will be evaluated monthly regarding:

- Serum creatinine, creatinine clearance. .1
- 24 hour proteinuria, protein/creatinine ratio. .2
- Fasting, random and postprandial glucose levels. .3
 - CNI trough level if used. .4
 - Urine analysis. .5
 - HGB level. .6
 - Uric acid, lipid profile. .7
 - Lupus serology. .8

Cardiovascular assessment: .9

ECCHO.

Atherosclerosis and vascular calcification incidence (NCCT model).

Regular measurement of blood pressure each visit.

Outcomes:

- Effect of dapagliflozin compared to placebo on eGFR. .1
- Effect of dapagliflozin compared to placebo on systolic/diastolic blood .2 pressure.
 - Effect of dapagliflozin compared to placebo on body weight. .3
- Safety of dapagliflozin vs. placebo the number of hypoglycemia .4 episodes between groups and serious adverse events.

Statistical Analysis:

Qualitative data were displayed in cross tabulations, and quantitative data were described in terms of arithmetic mean ± SD. Bivariate techniques were used for initial evaluation of contrasts. Thus, the chi-square and Fisher's exact tests were used for comparisons of frequencies of qualitative variables; the Mann-Whitney test and the unpaired t-test were used for comparisons of means of two quantitative variables. A p-value <0.05 was considered significant. Graft and patient survival rates were assessed using the Kaplan-Meier method. All analyses were carried out using the computer package SPSS for windows, release 16 SPSS Inc. Chicago, III, USA.

Administrative design •

Informed consent will be obtained from all subjects and the approval will be obtained from institutional review board (IRB) in Faculty of Medicine, Mansoura University. There is no funding.

Research question

The main research question is: Does use of SGLT2i will show superiority over conventional lines of treatment of lupus nephritis patient as regard efficacy and safety.

Rationale and justification

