The rational of this study is that SGLT2i are now one of the common lines in regression of chronic kidney disease either is diabetic or not.

Large trials on this issue exclude patient with glomerulonephritis, so we will study its renal efficacy in patient with secondary glomerulonephritis to SLE to prove their efficacy and safety in this group of patients.

Objectives

The main objective of this study is to:

- To compare use of SGLT2i versus standard care in regression of chronic kidney disease in patient with LN.
 - To study the safety and efficacy of this drug group with use of immunosuppression and possible interaction.

Hypothesis

leading causes SLE is the one of the of secondary glomerulonephritis. Despite the use immunosuppressive and antiproteinuric drugs, a number of patients are at risk of progressing to end-stage kidney disease. Additional therapies to slow kidney function decline are highly desired. The DAPA-CKD trial demonstrated that the sodium glucose co-transporter 2 inhibitor dapagliflozin significantly reduced the risk of kidney failure and prolonged survival in participants with chronic kidney disease with and without type 2 diabetes. The DAPA-CKD population excluded patients with lupus nephritis, so we determined the long-term efficacy and safety of dapagliflozin on major

kidney and cardiovascular outcomes in these patients.

References

- James Matera, DO. SGLT2 Inhibitors and CKD in -1 2021. Consultant360. Published online May 25, 2021.
- Dan Xu, Owain Chandler, Cleo Wee, et al. Sodium--2
 Glucose Cotransporter-2 Inhibitor (SGLT2i) as a Primary
 Preventative Agent in the Healthy Individual: A Need of
 August 2021
- Hiddo J.L. Heerspink, Ph.D., Bergur V. Stefánsson, et-3al. Dapagliflozin in Patients with Chronic Kidney Disease.N Engl J Med 2020; 383:1436-1446.
- Kana N. Miyataa, Shao-Ling Zhanga John S.D. Chana-4. The Rationale and Evidence for SGLT2 Inhibitors as a-4Treatment for Nondiabetic Glomerular Disease.CJASN May 2017, 12 (5) 825-835.
- Salem Almaani, Alexa Meara and Brad H. -5 Rovin. Update on Lupus Nephritis Clin PharmacolTher 2007;81:228-34. 10.1038/sj.clpt.6100039.

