Statistical Analysis Plan

Document Control

Title: Statistical Analysis Plan for the Study of SGLT2 Inhibitors in Lupus Nephritis Patients

Protocol ID: [NCT05748925] Version: 1.0 Date: [11/3/2024] Principal Investigator: [[name]] Statistician: [[name]] Approval Signatures: Principal Investigator: [name] Statistician: [name]

Table of Contents

- 1. Introduction
- 2. Study Design
- 3. Study Objectives
- 4. Endpoints
- 5. Sample Size Justification
- 6. Statistical Methods
- 7. Handling of Missing Data
- 8. Interim Analysis
- 9. Safety Analysis
- 10. Data Quality and Management
- 11. Software
- 12. Appendices

1. Introduction

• **Purpose of the SAP**: This document outlines the statistical approach for analyzing data from the clinical trial studying the effects of SGLT2 inhibitors on renal, cardiovascular, and hematological outcomes in lupus nephritis patients.

2. Study Design

Design: Randomized, double-blind, placebo-controlled clinical trial.

Study Duration: Conducted from September 2022 to November 2023

Randomization: Patients were randomly assigned to either dapagliflozin (10 mg once daily) or placebo groups using computer-generated random tables in a 1:1 ratio stratified by age and gender.

Blinding: The study was double-blinded, and all trial staff and participants remained unaware of individual treatment assignments until study completion.

3. Study Objectives

Primary Objective: To evaluate the impact of SGLT2 inhibitors on renal, cardiovascular, and hematological parameters in lupus nephritis patients.

Secondary Objective: To explore changes in body weight, BMI, and other echocardiographic and iron profile parameters over 12 months.

4. Endpoints

Primary Endpoints

Renal Function: Serum creatinine, eGFR, and 24-hour urine protein

Cardiovascular Health: BNP levels and coronary calcification via NCCT

Hematological Parameters: Hemoglobin and erythropoietin levels

Hepcidin Level: Measured before and after intervention

Secondary Endpoints

Body Weight and BMI: Assessed at baseline and follow-up visits.

Echocardiographic Findings: Assessed pre- and post-intervention.

Iron Profile: Serum ferritin and TSAT

5. Sample Size Justification

Calculation: A sample size of 100 patients was targeted, accounting for potential dropouts, to provide sufficient power (80%) at a significance level of 0.05 to detect differences between the two groups.

6. Statistical Methods

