
General Considerations

Significance Level: A two-sided alpha level of 0.05 will be used for all primary analyses.

Analysis Populations:

Intent-to-Treat (ITT): All randomized patients will be analyzed according to their assigned group.

Per-Protocol (PP): Only patients completing the study without major protocol violations.

Primary Endpoint Analysis

Renal Outcomes: ANOVA for repeated measures for serum creatinine and eGFR if normally distributed, and the Friedman test for non-normally distributed data. Post-hoc tests using Bonferroni correction.

Cardiovascular Outcomes: Mann-Whitney U test for BNP levels and coronary calcification between groups.

Hematological Outcomes: Paired t-test for hemoglobin and erythropoietin levels if data is normally distributed; otherwise, Wilcoxon signed-rank test.

Secondary Endpoint Analysis

Body Weight and BMI: Compared over time using ANOVA for repeated measures.

Echocardiographic Parameters: Analyzed with paired t-tests, adjusted with Bonferroni correction.

Iron Profile: Analyzed pre- and post-intervention using ANOVA or Kruskal-Wallis for non-normally distributed variables.

Categorical Variables

Chi-Square Test: For between-group comparisons of categorical data (e.g., presence of diabetes, hypertension).

7. Handling of Missing Data

Imputation: Last observation carried forward (LOCF) for data missing at random; multiple imputation for extensive missing data.

Sensitivity Analysis: Conducted to evaluate the robustness of primary endpoint findings against different missing data assumptions.

8. Interim Analysis

Timing: An interim analysis is planned at the halfway point (6 months).

Stopping Rules: An O'Brien-Fleming approach will be applied to adjust the significance threshold for interim testing, allowing for an earlier stop for efficacy or safety concerns.

9. Safety Analysis

Adverse Events (AEs): Summarized by type, frequency, and severity. Fisher's exact test will be used to compare AE rates between groups.

Specific Safety Parameters: Monitoring for hypotension, electrolyte imbalances, and kidney function.

10. Data Quality and Management

Data Quality Measures: Includes data verification, regular audits, and query resolution.

Database Lock: Data will be locked and verified prior to the final analysis.

11. Software

Statistical Software: All analyses will be conducted using SPSS (Version 25).

12. Appendices

	Control group. (n= 41)	Study group. (n= 38)	P value

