Age (years) Mean ± SD	36.6 ± 9.6	38±9.8	0.8
Sex No. (%) - Male - Female	7 (17.1%) 34 (82.9%)	4 (10.5%) 34 (89.5%)	0.5
Body weight (Kg) mean ± SD	78.9 ± 14	90 ± 15	0.5
Body mass index (Kg/m ²) mean ± SD	30.6 ± 10.5	33±5.7	0.6
Hypertension No. (%)	37 (90.2%)	38 (100%)	0.1
Diabetes No. (%)	7 (17.1%)	11 (28.9%)	0.2

Table (1): Demographics and associated medical disorders:

(Student T test or Mann-Whitney) for continuous data, and chi-square test for categorical data. Continuous data are expressed as mean (SD) or median (minimum – maximum). Categorical data are expressed as number (percentage), Level of significance < 0.05.

Table (2): SLE characteristics:

	Control group. (n= 41)	Study group. (n= 38)	P value
Disease duration (years) Median (min, max)	6 (1, 20)	7(1,19)	0.3

Lupus nephritis class No.			
(%)			
- Class I	1 (2.4%)	1 (2.6%)	
- Class II	2 (4.9%)	7 (18.4%)	0.1
- Class III	11 (26.8%)	8 (21.1%)	0.1
- Class IV	26 (36.4%)	16 (42.1%)	
- Class V	5 (2.4%)	1 (13.2%)	
- Class VI	0 (0%)	1 (2.6%)	
Activity index Median	6 (0, 10)	6 (0, 21)	0.8
(min, max)	0 (0, 19)	0 (0, 21)	0.8
Chronicity index Median	2(0, 8)	5 (0, 14)	0.2
(min, max)	2 (0, 8)	5 (0, 14)	0.2
Anti- phospholipid No.	6 (14 6%)	3 (7.0%)	0.4
(%)	0 (14.070)	5 (7.970)	0.4
Immunosuppressive			
medications No. (%)			
- Steroid + MMF	27 (65.9%)	18 (47 4%)	
- Steroid + CNI	5 (12.2 %)	4(10.5%)	0.2
- Steroid + CNI + MMF	2 (4.9 %)	1 (2 6%)	0.2
- Steroid + Azathioprine	7 (17.1%)	14(36.8%)	
- Steroid	0 (0%)	1 (2 6%)	
		1 (2.070)	
Cyclophosphamide No.	7 (17 1%)	5 (13.2%)	0.7
(%)	(1,11,0)		
Other medications No. (%)			
- Aspirin	15 (36.6%)	18 (34.4%)	0.3
- Statins	30 (73.2%)	24 (63.2%)	0.4
- Allopurinol	10 (24.4%)	14 (36.8%)	0.3
- ACEI/ARBS	26 (63.4%)	27(71.1%)	0.4
- Diuretics	14 (34.1%)	16 (32.1%)	0.3

MMF: mycophenolate mofetil; CNI: calcineurin inhibitors; ACEI/ARBS: angiotensin converting enzyme inhibitors/angiotensin receptor blockers; (Student T test or Mann-Whitney) for continuous data, and chi-square test for categorical data. Continuous data are expressed as mean (SD) or median (minimum – maximum). Categorical data are expressed as number (percentage).; Level of significance < 0.05.

	Control group. (n= 41)	Study group. (n= 38)	P value
Consumed C3 & C4 No. (%)	5 (12.2%)	2 (5.3%)	0.4

S. creatinine (mg/dL) Median (min, max)	0.8 (0.4, 2.7)	0.8 (0.4, 2.6)	0.8
24- hour urinary protein (g/24 hours) mean ± SD	0.4 (0.06-3.6)	0.6 (0.07-3)	0.3
eGFR (ml/min/m ²) mean ± SD	114 ± 51	128 ± 59.7	0.6

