End diastolic volume; Chi square test; Student t- test; Man, Whitney test; Level of significance < 0.05.

Table (10): Comparison between both groups as regard post intervention side effects

	Control group. (n= 41)	Study group. (n=38)	P value
AKI episodes No. (%)			
- No	38 (92.7%)	31 (81.6%) 5 (13.2%)	0.17
- once	1 (2.4%) 2 (4.9%)	2 (5.3%)	
- twice			
UTI No. (%)			
- No	35 (85.4%) 4 (9.8%)	31 (81.6%) 5 (13.2%)	0.8
- once	2 (4.9%)	2 (5.3%)	
- more than once			
Gynecological infection No. (%)	1 (2.4%)	2 (5.3%)	0.6
Viral infection No. (%)	1(2.4%)	1 (2.6%)	1
MMF intolerance No. (%)	1 (2.5%)	2 (5.3%)	0.6
Renal biopsy No. (%)	2 (4.9%)	1 (2.6%)	0.6
Increase steroid dose No. (%)	7 (17.1%)	4 (10.5%)	1

UTI: urinary tract infection episodes; AKI: acute kidney injury; chi-square test for categorical data. Categorical data are expressed as number (percentage).; Level of significance < 0.05.

figure1: flow chart of participating populations

Figure (2) shows difference between individual which had improved eGFR or not as regard to their basal eGFR in total cohort, which found that improving eGFR had been occurred in patients with lower eGFR (107±50 vs 137±58 ml/min/m²

Figure (3) show no significant difference between the drug and placebo groups (p=0.857). as regard incidence of anemia before intervention, the drug group has 23 anemic participants (60.5%) versus 24 participants (58.5%) in the placebo group, while post intervention, In the anemia category, the drug group has 16 participants (42.1%), while the placebo group has 22 participants (53.7%) with non-significant differences (p = 0.3)

Figure (4) differences in body weight between both groups at different time points:

Glossary of Terms and Abbreviations

AA	Amino Acids
ABIN	A20 Binding Inhibitor Of NF-Kb
ACE	Angiotensin-Converting Enzyme Inhibitors
ACR	American College of Rheumatology
AKI	Acute Kidney Injury
ALCAM	Activated Leucocyte Adhesion Molecule
ALP	Alkaline Phosphatase
AMP	Adenosine Monophosphate
АМРК	Amp-Activated Protein Kinase
ANA	Antinuclear Antibodies
ANG II	Angiotensin 2
ANOVA	Analysis Of Variance
ANTI-DSDNA	Anti Double Stranded Deoxyribonucleic Acid
	Antibodies
ANTI-SM	Anti-Smith Antibodies
APLS	Antiphospholipid Syndrome
ARBS	Angiotensin 2 Receptor Blockers
ATN	Acute Tubular Necrosis
ATP	Adenosine Triphosphate
BAFF	B-Cell-Activating Factor
BLISS	B Lymphocyte Stimulator Inhibitor Belimumab
	Plus Standard Therapy
BMI	Body Mass Index
BNP	Brain Natriuretic Peptide
BP	Blood Pressure

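### Four entries in SAP Table 2 contradict their own counts or totals, and Table 10 gives MMF intolerance only on whole arms although MMF use differs between them

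*Protocol*

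**What the plan says.** - **Protocol, Objectives.** The second objective reads "To study the safety and efficacy of this drug group with use of immunosuppression and possible interaction". The list of monthly assessments includes "CNI trough level if used".
- **SAP sections 3 to 9.** There is no analysis by immunosuppressive regimen, no interaction test and no analysis of CNI trough. The populations are per-protocol and ITT, the latter defined as "All randomized patients will be analyzed according to their assigned group". Adverse event rates are to be compared by Fisher's exact test.
- **SAP section 12, Table 2.** The columns are headed "Control group. (n= 41") and "Study group. (n= 38"). Control versus study, the table prints diuretics 14 (34.1%) and 16 (32.1%), p 0.3; aspirin 15 (36.6%) and 18 (34.4%), p 0.3; class IV 26 (36.4%) and 16 (42.1%); class V 5 (2.4%) and 1 (13.2%). One p of 0.1 covers all classes. MMF appears in two regimens: with steroid (27 and 18) and with steroid and CNI (2 and 1).
- **SAP section 12, Table 10.** The row "MMF intolerance No". (%) gives 1 (2.5%) and 2 (5.3%), p 0.6, under the same whole-arm headings.

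**The concern.** A baseline table is read to judge whether the arms are comparable, and most readers look at the percentages. Here several percentages do not follow from the counts beside them. In three rows the printed percentages point the opposite way from the counts. Two of those rows are co-medications and one is the most frequent histological class, in a trial whose main outcomes are renal.

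MMF intolerance raises a different issue. The rate is informative only among people exposed to MMF. If exposure differs between arms, a whole-arm denominator dilutes the two rates unequally. This bears on an objective about background immunosuppression for which the SAP plans no analysis.

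**Working it through.** **Inputs.** Column sizes 41 and 38, with counts, percentages and p-values from SAP Tables 2 and 10. Percentage = count / column n. Differences are study minus control.

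**1. Percentages in Table 2**

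| Row | Printed, control vs study | From counts, control vs study | Printed difference | Difference from counts |
|---|---|---|---|---|
| Diuretics | 34.1% vs 32.1% | 14/41 = 34.1% vs 16/38 = 42.1% | -2.0 | +8.0 |
| Aspirin | 36.6% vs 34.4% | 15/41 = 36.6% vs 18/38 = 47.4% | -2.2 | +10.8 |
| Class IV | 36.4% vs 42.1% | 26/41 = 63.4% vs 16/38 = 42.1% | +5.7 | -21.3 |

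Missing data cannot explain the gaps. The denominators implied by the printed percentages are 16/0.321 = 49.8, 18/0.344 = 52.3 and 26/0.364 = 71.4, each larger than its arm. For class IV, 36.4 is 63.4 with digits transposed. The printed control class percentages sum to 2.4 + 4.9 + 26.8 + 36.4 + 2.4 + 0 = 72.9. With 63.4 in place of 36.4 they sum to 99.9.

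**2. Class V counts**

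- As printed, control: 1 + 2 + 11 + 26 + 5 + 0 = 45, not 41.
- As printed, study: 1 + 7 + 8 + 16 + 1 + 1 = 34, not 38.
- With the class V counts exchanged: 41 and 38 exactly.
- The exchanged counts give 1/41 = 2.4% and 5/38 = 13.2%, which are the printed percentages.
- Pearson chi-square over the six classes: p = 0.10 with exchanged counts and 0.16 with printed counts. The printed value is 0.1.

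**3. Tests on the printed counts (class V exchanged)**

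| Row | Chi-square | Fisher | Printed p |
|---|---|---|---|
| Aspirin | 0.33 | 0.37 | 0.3 |
| Diuretics | 0.47 | 0.50 | 0.3 |
| Class IV alone | 0.058 | 0.07 | none |
| Class V alone | 0.07 | 0.10 | none |

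The aspirin p fits its counts. The diuretic p fits neither test, nor the continuity-corrected chi-square (0.62). A count near the printed percentage does not rescue it: 12/38 = 31.6% gives chi-square p = 0.81.

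**4. MMF intolerance**

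- Whole arm: 1/41 = 2.4% (printed 2.5%, which fits 1/40) and 2/38 = 5.3%. Fisher p = 0.61, which matches the printed 0.6. The difference is +2.8 points.
- MMF at baseline: 27 + 2 = 29 of 41 (70.7%) and 18 + 1 = 19 of 38 (50.0%).
- Among those users: 1/29 = 3.4% and 2/19 = 10.5%. The difference is +7.1 points.
- Newcombe interval: Wilson limits are 0.6% to 17.2% (control) and 2.9% to 31.4% (study). Lower limit 7.1 - sqrt((10.5 - 2.9)² + (17.2 - 3.4)²) = -8.6. Upper limit 7.1 + sqrt((31.4 - 10.5)² + (3.4 - 0.6)²) = +28.1. These limits come from unrounded inputs, so the rounded figures shown can differ in the last digit. Fisher p = 0.55.
- Restricted to the steroid + MMF regimen: 1/27 = 3.7% and 2/18 = 11.1%, Fisher p = 0.55.

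**The case against.** **Nothing is concealed, and nothing becomes significant.** The counts for diuretics, aspirin and class IV are printed beside the wrong percentages, and for class V the percentages are right. The aspirin and overall class p-values agree with the correct data. No corrected comparison in these rows is below 0.05. All of this stands and limits the weight of the point. It does not make the percentages right.

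**The whole-arm denominator follows the SAP.** The ITT set is all randomised patients and adverse events are compared between groups. This stands too: the figure is a poor choice for this event rather than a miscalculation, apart from 2.5% in place of 2.4%. There are only three events, and Fisher p moves only from 0.61 to 0.55.

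**The text may have been damaged in reading.** Table 2 shows such damage elsewhere, for example in the antiphospholipid row. This is a fair caution for the diuretic and aspirin cells. It is unlikely for class V, where one exchange repairs both totals and both percentages, and for class IV, where two digits are transposed.

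**Stronger readings a reader might infer:**

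- *The objective rests on these cells.* It does not. Aspirin, diuretics and class are not immunosuppression. The regimen rows sum to 41 and 38, and their p of 0.24 matches the printed 0.2. Nor is MMF intolerance the only related result, since Table 10 also reports steroid increases.
- *MMF intolerance was impossible in the 31 patients not on MMF at baseline.* Table 2 gives baseline regimens only, and patients may have switched.
- *Diuretic use relates to AKI.* AKI occurred in 3 control and 7 study patients (Fisher p = 0.18), and no document links the two.
- *Azathioprine use is significantly unbalanced.* For 7/41 versus 14/38, chi-square gives 0.047 and Fisher 0.07. This is one regimen of five, picked after seeing the data, and both figures are printed correctly.

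**Conclusion.** The point holds as a correction to reported figures. Four Table 2 entries are internally wrong: three percentages and one pair of exchanged counts. Three of the four reverse the visible direction between arms, the largest being class IV at 63.4% versus 42.1%, where print shows 36.4% versus 42.1%. The diuretic row has a further fault, because its p-value does not follow from its counts, so 42.1% is conditional on the count of 16 being right.

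MMF intolerance among baseline users is 3.4% versus 10.5%. The interval of -8.6 to +28.1 points is too wide to support any conclusion about an effect of treatment. The change matters for description, not inference.

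The interaction objective is a separate gap: it is stated in the protocol and has no planned analysis in the SAP.

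Assumptions: the Table 2 counts are correct except for class V, and MMF users are those on MMF at baseline (29 and 19, or 27 and 18 if only steroid + MMF is counted).

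**What to change.** 1. **Table 2.** Correct the four entries from source data. The expected values are aspirin 47.4%, class IV control 63.4%, class V 1 (2.4%) and 5 (13.2%), and diuretics 42.1% if the count of 16 is confirmed. Check that count and recompute the diuretic p-value.
2. **Table 10.** Keep the whole-arm figure for MMF intolerance, with 1/41 as 2.4%. Beside it, add the rate among patients ever on MMF (29 and 19 at baseline, plus any who switched to it), with a 95% CI for the difference.
3. **Objective.** State the immunosuppression-interaction objective as descriptive, because the SAP plans no analysis for it.

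The cost is a check of a few cells and one extra line in a table, using baseline data already held and a record of regimen changes. The downside is that the arms look less balanced and the MMF intolerance rate less favourable.

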Statistical Analysis Plan

Document Control

Title: Statistical Analysis Plan for the Study of SGLT2 Inhibitors in Lupus Nephritis Patients

Protocol ID: [NCT05748925] Version: 1.0 Date: [11/3/2024] Principal Investigator: [[name]] Statistician: [[name]] Approval Signatures: Principal Investigator: [name] Statistician: [name]

Table of Contents

- 1. Introduction
- 2. Study Design
- 3. Study Objectives
- 4. Endpoints
- 5. Sample Size Justification
- 6. Statistical Methods
- 7. Handling of Missing Data
- 8. Interim Analysis
- 9. Safety Analysis
- 10. Data Quality and Management
- 11. Software
- 12. Appendices

1. Introduction

• **Purpose of the SAP**: This document outlines the statistical approach for analyzing data from the clinical trial studying the effects of SGLT2 inhibitors on renal, cardiovascular, and hematological outcomes in lupus nephritis patients.

2. Study Design

Design: Randomized, double-blind, placebo-controlled clinical trial.

Study Duration: Conducted from September 2022 to November 2023

Randomization: Patients were randomly assigned to either dapagliflozin (10 mg once daily) or placebo groups using computer-generated random tables in a 1:1 ratio stratified by age and gender.

Blinding: The study was double-blinded, and all trial staff and participants remained unaware of individual treatment assignments until study completion.

3. Study Objectives

Primary Objective: To evaluate the impact of SGLT2 inhibitors on renal, cardiovascular, and hematological parameters in lupus nephritis patients.

Secondary Objective: To explore changes in body weight, BMI, and other echocardiographic and iron profile parameters over 12 months.

4. Endpoints

Primary Endpoints

Renal Function: Serum creatinine, eGFR, and 24-hour urine protein

Cardiovascular Health: BNP levels and coronary calcification via NCCT

Hematological Parameters: Hemoglobin and erythropoietin levels

Hepcidin Level: Measured before and after intervention

Secondary Endpoints

Body Weight and BMI: Assessed at baseline and follow-up visits.

Echocardiographic Findings: Assessed pre- and post-intervention.

Iron Profile: Serum ferritin and TSAT

5. Sample Size Justification

Calculation: A sample size of 100 patients was targeted, accounting for potential dropouts, to provide sufficient power (80%) at a significance level of 0.05 to detect differences between the two groups.

6. Statistical Methods

General Considerations

Significance Level: A two-sided alpha level of 0.05 will be used for all primary analyses.

Analysis Populations:

Intent-to-Treat (ITT): All randomized patients will be analyzed according to their assigned group.

Per-Protocol (PP): Only patients completing the study without major protocol violations.

Primary Endpoint Analysis

Renal Outcomes: ANOVA for repeated measures for serum creatinine and eGFR if normally distributed, and the Friedman test for non-normally distributed data. Post-hoc tests using Bonferroni correction.

Cardiovascular Outcomes: Mann-Whitney U test for BNP levels and coronary calcification between groups.

Hematological Outcomes: Paired t-test for hemoglobin and erythropoietin levels if data is normally distributed; otherwise, Wilcoxon signed-rank test.

Secondary Endpoint Analysis

Body Weight and BMI: Compared over time using ANOVA for repeated measures.

Echocardiographic Parameters: Analyzed with paired t-tests, adjusted with Bonferroni correction.

Iron Profile: Analyzed pre- and post-intervention using ANOVA or Kruskal-Wallis for non-normally distributed variables.

Categorical Variables

Chi-Square Test: For between-group comparisons of categorical data (e.g., presence of diabetes, hypertension).

7. Handling of Missing Data

Imputation: Last observation carried forward (LOCF) for data missing at random; multiple imputation for extensive missing data.

Sensitivity Analysis: Conducted to evaluate the robustness of primary endpoint findings against different missing data assumptions.

8. Interim Analysis

Timing: An interim analysis is planned at the halfway point (6 months).

Stopping Rules: An O'Brien-Fleming approach will be applied to adjust the significance threshold for interim testing, allowing for an earlier stop for efficacy or safety concerns.

9. Safety Analysis

Adverse Events (AEs): Summarized by type, frequency, and severity. Fisher's exact test will be used to compare AE rates between groups.

Specific Safety Parameters: Monitoring for hypotension, electrolyte imbalances, and kidney function.

10. Data Quality and Management

Data Quality Measures: Includes data verification, regular audits, and query resolution.

Database Lock: Data will be locked and verified prior to the final analysis.

11. Software

Statistical Software: All analyses will be conducted using SPSS (Version 25).

12. Appendices

	Control group. (n= 41)	Study group. (n= 38)	P value
Age (years) Mean ± SD	36.6 ± 9.6	38±9.8	0.8
Sex No. (%) - Male - Female	7 (17.1%) 34 (82.9%)	4 (10.5%) 34 (89.5%)	0.5
Body weight (Kg) mean ± SD	78.9 ± 14	90 ± 15	0.5
Body mass index (Kg/m ²) mean ± SD	30.6 ± 10.5	33±5.7	0.6
Hypertension No. (%)	37 (90.2%)	38 (100%)	0.1
Diabetes No. (%)	7 (17.1%)	11 (28.9%)	0.2

Table (1): Demographics and associated medical disorders:

(Student T test or Mann-Whitney) for continuous data, and chi-square test for categorical data. Continuous data are expressed as mean (SD) or median (minimum – maximum). Categorical data are expressed as number (percentage), Level of significance < 0.05.

Table (2): SLE characteristics:

	Control group. (n= 41)	Study group. (n= 38)	P value
Disease duration (years) Median (min, max)	6 (1, 20)	7(1,19)	0.3

Lupus nephritis class No.			
(%)			
- Class I	1 (2.4%)	1 (2.6%)	
- Class II	2 (4.9%)	7 (18.4%)	0.1
- Class III	11 (26.8%)	8 (21.1%)	0.1
- Class IV	26 (36.4%)	16 (42.1%)	
- Class V	5 (2.4%)	1 (13.2%)	
- Class VI	0 (0%)	1 (2.6%)	
Activity index Median	6 (0, 10)	6 (0, 21)	0.8
(min, max)	0 (0, 19)	0 (0, 21)	0.8
Chronicity index Median	2(0, 8)	5 (0, 14)	0.2
(min, max)	2 (0, 8)	5 (0, 14)	0.2
Anti- phospholipid No.	6 (14 6%)	3 (7.0%)	0.4
(%)	0 (14.070)	5 (7.970)	0.4
Immunosuppressive			
medications No. (%)			
- Steroid + MMF	27 (65.9%)	18 (47 4%)	
- Steroid + CNI	5 (12.2 %)	4(10.5%)	0.2
- Steroid + CNI + MMF	2 (4.9 %)	1 (2 6%)	0.2
- Steroid + Azathioprine	7 (17.1%)	14(36.8%)	
- Steroid	0 (0%)	1 (2 6%)	
		1 (2.070)	
Cyclophosphamide No.	7 (17 1%)	5 (13.2%)	0.7
(%)	(1,11,0)		
Other medications No. (%)			
- Aspirin	15 (36.6%)	18 (34.4%)	0.3
- Statins	30 (73.2%)	24 (63.2%)	0.4
- Allopurinol	10 (24.4%)	14 (36.8%)	0.3
- ACEI/ARBS	26 (63.4%)	27(71.1%)	0.4
- Diuretics	14 (34.1%)	16 (32.1%)	0.3

MMF: mycophenolate mofetil; CNI: calcineurin inhibitors; ACEI/ARBS: angiotensin converting enzyme inhibitors/angiotensin receptor blockers; (Student T test or Mann-Whitney) for continuous data, and chi-square test for categorical data. Continuous data are expressed as mean (SD) or median (minimum – maximum). Categorical data are expressed as number (percentage).; Level of significance < 0.05.

	Control group. (n= 41)	Study group. (n= 38)	P value
Consumed C3 & C4 No. (%)	5 (12.2%)	2 (5.3%)	0.4

S. creatinine (mg/dL) Median (min, max)	0.8 (0.4, 2.7)	0.8 (0.4, 2.6)	0.8
24- hour urinary protein (g/24 hours) mean ± SD	0.4 (0.06-3.6)	0.6 (0.07-3)	0.3
eGFR (ml/min/m ²) mean ± SD	114 ± 51	128 ± 59.7	0.6
Cholesterol mg/dL mean ± SD	185 ± 46	172 ± 40.7	0.5
Albumin (g/dL) mean ± SD	3.7 ± 0.4	3.7 ± 0.3	0.4
Random blood sugar (mg/dL) Median (min, max)	89 (66, 568)	92.5 (64, 243)	0.4
Uric acid (mg/dL) mean ± SD	6.2 ± 2.1	6.5 ± 1.7	0.2
Alanine aminotransferase (IU/L) Median (min, max)	17 (2, 84)	17 (7, 82)	0.8
Aspartate aminotransferase (IU/L) Median (min, max)	21(9, 66)	19 (12,72)	0.4
Sodium (mEq/L) mean ± SD	137 ± 3.1	136 ± 3	0.5
Potassium (mEq/L) mean ± SD	3.9 ± 0.4	4 ± 0.4	0.3

eGFR: estimated glomerular filtration rate; (Student T test or Mann-Whitney) for continuous data, and chisquare test for categorical data. Continuous data are expressed as mean (SD) or median (minimum – maximum). Categorical data are expressed as number (percentage). Level of significance < 0.05.

Table (4): Baseline hematological findings:

	Control group. (n= 41)	Study group. (n= 38)	P value		
Hemoglobin (g/dL) Mean \pm SD	11.9 ± 1.9	11.7 ± 1.7	0.5		
MCV (FL) Mean ± SD	82 ± 7	84 ± 6.9	0.9		
MCH (Pg) Mean ± SD	25.4 ± 2.9	26.3 ± 2.9	0.9		
Ferritin (mg/dL) Median (min, max)	60 (13, 1113)	33.5 (3, 1460)	0.09		
TSAT (%) Median (min, max)	23.8 (7, 64)	18 (6, 74)	0.05		
Erythropoietin level (IU/L) Mean ± SD	11.6 ± 2.1	11.3 ± 1.4	0.1		
Hepcidinlevel(ug/L) $Mean \pm SD$	198 ± 74	182 ± 76	0.3		
Platelet count (*10 ³) Mean \pm SD	288 ± 71	300 ± 79	0.7		

McW Mean corpuscle volume; MCH: Mean corpuscular hemoglobin; TSAT: Transferrin saturation test; (Student T test or Mann-Whitney) for continuous data, and chi-square test for categorical data. Continuous data are expressed as mean (SD) or median (minimum – maximum). Categorical data are expressed as number (percentage).; Level of significance < 0.05.

Table (5): Baseline Cardiac evaluation:

Control group. Study group. P value

	(n= 41)	(n= 38)	
Coronary calcification No. (%)	3 (7.3%)	11 (28.9%)	0.012
Coronary calcification severity No. (%) - No - Minimal - Mild - moderate	38 (92.7%) 1 (2.4%) 1 (2.4%) 1 (2.4%)	27 (71.1%) 3 (7.9%) 7 (18.4%) 1 (2.6%)	0.04
BNP (ng/L) Median (min, max)	52 (40, 557)	52 (34, 90)	0.8
Echocardiographic	c finding		0.6
EF % Mean \pm SD	65.4 ± 9.3	64.6 ± 5.4	0.6
LAD (ml) Mean ± SD	24.2 ± 7.6	24.9 ± 7.6	0.6
Aortic diameter (ml) Mean ± SD	24.7±7.4	24.8±7.1	0.9
ESV (ml/m) Median (min, max)	38±13.6	41±13.9	0.4
EDV (ml/m) Mean ± SD	98±35.7	111.5±31.6	0.08

BNP: Brain natriuretic peptide; EF: Ejection fraction; LAD: Left atrial dimension; ESV: End-systolic volume; EDV: End diastolic volume; (Student T test or Mann-Whitney) for continuous data, and chi-square test for categorical data. Continuous data are expressed as mean (SD) or median (minimum – maximum). Categorical data are expressed as number (percentage).; Level of significance < 0.05.

Table (6): Comparison between study and control groups as regard effect of intervention on
 disease activity and renal affection at different time points

	Grouping	Baseline	3 months	6 months	9 months	12 months	P value*
Consumed C3 & C4	Control	5 (12.2%)	5 (12.2%)	4 (9.8%)	6 (14.6%)	10 (24.4%)	0.1
No. (%)	Study	2 (5.3%)	5 (13.2%)	2 (5.3%)	6 (15.8%)	6 (15.8%)	0.1
	P value**	0.4	0.9	0.3	1	0.4	
S. creatinine (mg/dL)	Control	0.8 (0.4, 2.7)	0.9 (0.4, 3.1)	0.9 (0.3- 3.1)	0.9 (0.6, 4)	0.9 (0.6, 5)	0.1
Median (min, max)	Study	0.8 (0.4, 2.6)	0.9 (0.6, 2.6)	0.9 (0.5, 3.1)	1 (0.5, 4.2) a	0.9 (0.5, 5)	0.01
	P value**	0.8	0.8	1	0.5	0.8	
eGFR (ml/min/m²) Mean ± SD	Control	114±51	104±45 a	107±53.8	99±47 a	100.3±44.5 a	0.003
	Study	128±59.7	115±47 A	118±50 A	109±44.5 a, c	115.7±48 a	0.001
	P value**	0.6	0.9	0.8	0.2	0.9	
	Control	0.4(0.06- 3.6)	0.6 (0.03-5)	0.6 (0.03- 7)	0.6 (0.02, 5)	0.5 (0.02 , 8)	0.06
24- hour urinary protein (g/24 hours) Median (min, max)	Study	0.6 (0.07-3)	0.7 (0.01-4)	0.8 (0.02, 4.8)	0.6 (0.05, 4.7)	0.5 (0.02 , 4)	0.07
	P value**	0.3	0.9	0.8	0.6	0.6	
Albumin (g/dL)	Control	3.7±0.4	3.7±0.4	3.6±0.4	3.8±0.4 c	3.9±0.3 a, b, c	0.001
iviean ± SD.	Study	3.7±0.3	3.7±0.5	3.7±0.3	3.8±0.3 c	3.9±0.8 a, c	0.04
	P value**	0.4	0.9	0.1	0.7	0.8	

(*) Within group analysis (repeated measure ANOVA).

(**) Between group analysis (Student T test or Mann-Whitney) for continuous data, and chi-square test for categorical data. Post-hoc analysis;

(a) significance against baseline <0.05; (b) significance against 3 months level <0.05, (c) significance against 6 months level <0.05, (d)

significance against 9 months level <0.05. Continuous data are expressed as mean (SD) or median (minimum – maximum). Categorical data are expressed as number (percentage).

Table (7): effect of intervention on hematological findings between both groups at different time points:

	Grouping	Baseline	3 months	6 months	9 months	12 months	P value*
Haemoglobin (g/dL) Mean ± SD	Control	11.9±1.9	12.2±1.9	11.8±2.5	12±1.9	12.2±1.9	0.08
	Study	11.8±1.8	12.3±1.7	12±2.5	11.9±2.2	12±2	0.06
	P value**	0.5	0.7	0.7	0.3	0.6	
MCV (FL) Mean ± SD	Control	82±7	83±7	84±7	84.6±7.9	81.5±13	0.1
	Study	84±6.9	80±14	83±10	83.2±10.8	84±7	0.3
	P value**	0.9	0.1	0.5	0.5	0.4	
MCH (Pg) Mean ± SD	Control	25.4±2.9	27.3±9.8	28.5±9	26.9±3.2	26.9±3.1	0.08
	Study	26.3±2.9	27.3±9.5	27±3	26.6±3.5	27.1±3.4	0.8
	P value**	0.9	0.9	0.4	0.4	0.5	

(*) Within group analysis (repeated measure ANOVA).

(**) Between group analysis (Student T test or Mann-Whitney) for continuous data, and chi-square test for categorical data. Continuous data are expressed as mean (SD) or median (minimum – maximum). Categorical data are expressed as number (percentage).

MCV: Mean corpuscle volume; MCH: Mean corpuscular haemoglobin.

Table (8): other hematological findings differences between both groups:

	Grouping	Baseline	12 months	P value*
Ferritin (mg/dL)	Control	60 (13, 1113)	75 (6, 2127)	0.5
Median (min, max)	Study	33.5 (3, 1460)	64 (3, 1311)	0.8
	P value**	0.09	0.4	
TSAT (%) Median	Control	23.8 (7, 64)	28 (5, 62)	0.1
	Study	18 (6, 74)	20 (6, 66)	0.9
	P value**	0.05	0.1	
Erythropoietin	Control	11.6±2.1	12.8 ± 3.5	0.08
SD	Study	11.3±1.4	12.4 ± 3.5	0.1
	P value**	0.1	0.6	
Hepcidin level ug/L	Control	198 ± 74	128 ±63	0.001
Mean ± SD	Study	182±76	116±15	0.001
	P value**	0.3	0.2	
Platelet count	Control	288 ± 71	283 ± 74	0.6
(×10³) Mean ± SD	Study	300 ± 79	276 ± 65	0.01
	P value**	0.7	0.5	

(*) Within group analysis (paired t test).

(**) Between group analysis (Student T test or Mann-Whitney) for continuous data, and chi-square test for categorical data.

Continuous data are expressed as mean (SD) or median (minimum – maximum). Categorical data are expressed as number (percentage).

TSAT: Transferrin saturation test

Table (9): Cardiac evaluation differences between both groups after 12 months:

	Control group	Study group	P value
Coronary calcification No. (%)	1 (2.4%)	11 (28.9%)	0.001
Coronary calcification severity No. (%) - No - Minimal - Mild - moderate	40 (97.6%) 0 0 1 (2.4%)	27 (71.1%) 9 (23.7%) 2 (5.3%) 0	0.002
BNP ng/L Mean \pm Sd	66 ± 22.1	65.8±21	0.9
Echocardiographic findi	ng		
EF % Mean ± SD	65.5±5.8	64.9±5.2	0.8
LAD ml Mean \pm SD	26.7±7.6	28.2±8.6	0.4
Aortic diameter ml Mean ± SD	26.6±6.5	25.5±6.2	0.4
ESV ml/min Mean ± SD	39.5±18	36.3±9.3	0.3
EDV ml/min Mean ± SD	108±29.6	109±19.3	0.9

BNP: Brain natriuretic peptide; EF: Ejection fraction; LAD: Left atrial dimension; ESV: End- systolic volume; EDV:

